20.7: COGNITIVELY IMPAIRED ADULTS, OR ADULTS WITH FLUCTUATING OR DIMINISHED CAPACITY TO CONSENT	36
20.8: ADULTS UNABLE TO CONSENT	37
CHAPTER 21 – SETTING	37
21.1: INTERNATIONAL RESEARCH.....	37
21.2: COMMUNITY-BASED PARTICIPATORY RESEARCH.....	37
21.3: RESEARCH SITES	38
CHAPTER 22 – MULTI-SITE RESEARCH	39
CHAPTER 23 – REFERENCES	40

ABBREVIATIONS

ANCOVA	Analysis of Covariance
CDC	Centers for Disease Control and Prevention
EASY	Exercise and Screening for You
IRB	Institutional Review Board
HIPAA	Health Insurance Portability and Accountability Act
NIA	National Institute on Aging
PA	Physical Activities
PHI	Patient Health Information
QOL	Quality of Life
SPPB	Short Physical Performance Battery
WMT	Wellness Motivation Theory
REDCap	Research Electronic Data Capture
RAPA	Rapid Assessment of Physical Activity
RA	Research Assistant
PROMIS	Patient-Reported Outcomes Measurement Information System
UMN	University of Minnesota
NNINR	National Institute of Nursing Research
RE-AIM	Reach- Effectiveness –Adoption- Implementation-Maintenance
SAS	A statistical analysis software
SPSS	A statistical analysis software

STUDY SUMMARY

Study Title	Community-based intervention effects on older adults' physical activity & falls
Study Design	2 x 2 factorial experimental design
Primary Objective	Determine which experimental intervention component(s) increase physical activity (PA) among community-dwelling older adults post-intervention: immediately, 6 months, and 12 months
Secondary Objective(s)	Determine which experimental intervention components decrease fall occurrence and increase quality of life (QOL) among community-dwelling older adults 12 months post-intervention
Primary Study Intervention or Interaction	An 8 week PA intervention that includes the following components: 
 1. Two sets of behavioral strategies: interpersonal and intrapersonal 2. Otago PA protocol 3. PA-monitor (Fitbit Accelerometers) 4. Attention Control Content: Health & Age Topics from the National Institute on Aging (NIA)
Study Population	Older adults \geq 70 years of age
Sample Size (number of participants)	N = 308
Study Duration for Individual Participants	15 to 18 months

CHAPTER 1- OBJECTIVES

1.1: PURPOSE

Purpose, specific aims, or objectives.

Our research team will conduct a 2 x 2 factorial experiment testing the individual and combined effects of two empirically and theoretically relevant sets of behavior change strategies on community-dwelling older adults' physical activity. To do this we will randomize participants ≥ 70 years old ($n = 308$) to 1 of 4 experimental conditions. All conditions include an evidence-based physical activity protocol endorsed by Centers for Disease Control and Prevention (CDC) for use by all older adults, including those with frailty and multiple co-morbidities and the commercially available physical activity monitor (e.g., Fitbit) to augment intervention delivery. Intervention components that are experimental and vary by condition are the sets of behavior change strategies which will be combined with the physical activity protocol and the physical activity monitor. Condition 1 has no specific behavior change strategies; Condition 2 includes an intervention component comprised of 5 interpersonal behavior change strategies, such as facilitating social support and social comparison; Condition 3 includes an intervention component comprised of 5 intrapersonal behavior change strategies, such as setting personally meaningful goals; and Condition 4 includes both sets of behavior change strategies -- 5 interpersonal strategies combined with 5 intrapersonal behavior change strategies.

To fully examine the effects of these experimental components, we have delineated Primary, Secondary and Exploratory Aims:

Primary Aim: Determine which experimental intervention component(s) increase PA among community-dwelling older adults post-intervention: immediately, 6 months, and 12 months.

Hypothesis: Participants receiving the interpersonal set of behavior change strategies will have clinically meaningful increases in PA post- intervention (at all 3 time-points), compared to participants not receiving these strategies.

Secondary Aim: Determine which experimental intervention component(s) decrease fall occurrence and increase quality of life (QOL) among community-dwelling older adults 12 months post-intervention. **Hypotheses:** Participants receiving the set of interpersonal behavior change strategies will have clinically meaningful reductions in falls and increases in QOL, 12 months post-intervention, compared to participants not receiving these strategies.

Exploratory Aim: Evaluate experimental intervention component effects on targeted psychosocial constructs (social support; readiness; self-regulation) and physical constructs (functional leg strength and balance), which are theorized as mechanisms of change--and whether these mechanisms mediate the effects of experimental intervention components on PA and falls. **Hypotheses:** Receiving the interpersonal behavioral change strategies, relative to not receiving these strategies, will elicit increases in targeted psychosocial constructs and increases in physical constructs, which in turn will mediate the intervention's effects on PA behavior and falls.

CHAPTER 2 - BACKGROUND

2.1 SIGNIFICANCE OF RESEARCH QUESTION/PURPOSE

A description of the relevant prior research and gaps in current knowledge for your research question.

Every year, 1 in 3 people aged 65 and older falls; 25% of which result in serious injury or death and have devastating effects on QOL.^{1,5} Despite evidence that PA targeting leg strength and balance reduce falls, less than 12% of older adults engage in these activities on a regular basis and fall rates continue to increase.⁷ Research examining intervention strategies that motivate older adults to engage in PA is scarce and inconclusive. There is a compelling need to identify specific behavioral change strategies that effectively and efficiently motivate older adults to sustain increased levels of PA.

Several behavioral change strategies have the potential to motivate older adults to engage in PA, such as facilitating social support;¹⁹ barriers management;²⁷ goal-setting;²⁸ habit formation;²⁹ and self-monitoring outcomes.³⁰ To date, intervention studies typically combine 7-10 strategies and evaluate them as part of an “intervention package” compared to a control group. Thus, it is not known which strategy, or set thereof, are effective and should be included in efficient and translatable interventions. The **objective of this proposal** is to **identify behavioral change strategies that elicit increased PA, sustained for 12 months and, in turn, lead to a reduction in falls and improved QOL**. Building on prior research, the proposed study will use a factorial experimental design to test the relative influence of behavioral change strategies separated into two components. These components are comprised of distinct sets of behavioral change strategies that represent two different ways of motivating people to take action: interpersonal and intrapersonal, consistent with theories of behavioral change^{16, 22} and lifespan development,⁴⁶ as well as empirical evidence.³³ The components will be combined with core intervention content that includes Otago,¹⁰ an evidence-based fall-reducing PA protocol, and a PA-monitor for self-tracking.

2.2 EXISTING LITERATURE

Scientific background for, rationale for, and significance of the research based on the existing literature and how will it add to existing knowledge.

Fall rates continue to increase and PA rates remain low among older adults. The complex public health problems of falls and inactivity create significant social and economic burdens. Every year, 1 in 3 people aged 65 and older falls; 25% result in serious injury or death.¹ Injurious and fatal fall rates increase exponentially with age, particularly after age 70.¹ Serious injuries caused by falls, such as traumatic brain injuries and fractures,² often require intense healthcare services within emergency rooms, hospitals, and nursing homes.³ They also increase fear of falling,⁴ decrease mobility, and decrease QOL.⁵ The direct healthcare costs of fall-related injuries in older adults are \$34 billion annually.¹ Decreased leg strength, poor balance, and altered gaits are the most common causes of falls. These causes can be mitigated with the regular practice of leg strengthening and balance-challenging activities.⁶ Walking and flexibility movements augment these activities. Previous research demonstrates that approximately 35% of injurious/fatal falls can be prevented with fall-reducing PA,⁶ and that PA is associated with improved QOL.⁵ Despite public health efforts to disseminate and implement this

evidence, less than 12% of people aged 65+ engage in PA as recommended⁷ and fall rates continue to rise. Thus, knowledge of fall-reducing PA has not translated to increased PA rates in the community of older adults, or made an impact on falls. *It is essential to augment what is known; the types and doses of PA that reduce falls, with what is not known; intervention strategies that motivate older adults to sustain increased PA.⁸*

Fall-reducing PA interventions. In a Cochrane review, Gillespie and colleagues identify fall-reducing PA among the most effective fall prevention interventions, yet few studies describe or evaluate strategies to increase “uptake” of and “adherence” to fall-reducing PA.⁶ The dozens of fall-reducing PA intervention studies conducted over the last several decades have generated substantial knowledge about which PAs work to reduce falls and injuries among older adults, including those with multiple chronic conditions, pain, and frailty.⁹ Meta-analyses show the effects of fall-reducing PA interventions on fall rate ratios range from 0.56 to 0.82.^{6,10,11} One example of an evidence-based program emerging from this literature is the Otago protocol, which is cost-effective when delivered 1:1 in home settings¹² and when delivered in small groups.¹³ Otago and other similar PA protocols include instruction and supervisory strategies, but not content to increase the initiation or maintenance of PA. The few intervention studies that have included such content show conflicting results due, in part, to the use of self-report PA measures.^{9,14} *Future studies need to build upon existing evidence-based, fall-reducing PA protocols by combining them with evidence-based strategies to motivate older adults' PA, and estimate their effects on objectively measured PA (e.g., accelerometer).* Below we identify fundamental building blocks that inform such progress.

Motivation for fall-reducing PA. Motivation, simply defined as why one moves to action, is a key determinant of older adults' PA and a dynamic process dependent on key constructs.¹⁵⁻¹⁸ For instance, social support for PA from important others (e.g., friends, neighbors, family, providers) is known to influence PA engagement.^{19,20} Readiness for PA refers to the identification of goals consistent with personal values and health-related behavior, as well as commitment and confidence for attaining those goals.^{21,22} Self-regulation refers to self-monitoring progress toward goal attainment,²³ identifying discrepancies between what is desired and what is achieved, and adjusting plans accordingly.²⁴ Together, as postulated by the wellness motivation theory (WMT),²⁵ and consistent with some research,²⁶ these constructs influence the maintenance of personally valued health behaviors, such as PA. Despite strong evidence and theoretical explanations of motivation as a PA determinant, there is a dearth of fall-reducing PA research that evaluates motivational constructs.^{6,9} *Motivational constructs, based on empirical evidence and theory, can be targeted in new multi- component fall-reducing PA interventions, using behavior change strategies.*

Which behavioral change strategies have potential to motivate older adults to sustain increased PA? Prior research, in the field of PA, indicates that many behavioral change strategies target motivational constructs and have the potential to increase older adults' PA, such as facilitating social support;¹⁹ barriers management;²⁷ goal-setting;²⁸ habit formation;²⁹ and self-monitoring outcomes.³⁰ To date, intervention studies have typically included 7-10 strategies and evaluate them as part of an “intervention package” compared to control groups. To address questions about which of these strategies have an impact on key outcomes, meta-analyses have been conducted to examine effects of individual and sets of similar behavioral change strategies, but show mixed results due to difficulties disentangling intervention content post- experiment.^{31,32} The studies do suggest that different strategies, or sets of strategies, may benefit older adults more than younger adults,³³ and may result in sustained increases in PA.³² A weakness of prior research is that it has not produced sufficient evidence to understand which

strategies should, or should not, be included in streamlined multicomponent fall-reducing interventions. A strength of prior research is that it highlights important methodological strategies that can be used in future research to improve reproducibility and scientific rigor, such as a) clearly describing each strategy used and how it is operationalized; and b) separating behavioral change strategies into distinct intervention components based on theoretical, empirical, and practical rationale, so that the contributions of each component may be examined experimentally.

Questions about which behavioral change strategies motivate older adults to sustain increased fall-reducing PA warrant factorial experimental design. Factorial experiments are a practical approach to optimizing interventions for effectiveness, efficacy, and translatability through the identification of intervention components that meaningfully contribute to overall intervention effects. Components refer to distinct intervention features related to content (e.g., sets of behavioral change strategies), delivery, or other logistics. Other experimental designs, such as multiple arm comparative experiments and two arm randomized controlled trials, cannot directly address specific questions about the individual and combined effects of intervention components, and thus would be inefficient in the context of investigating their relative contributions.³⁵ Factorial experiments are the best choice for future research that investigates combining fall-reducing PA interventions with behavioral change strategies, separated into distinct components, because these experiments enable answering questions about the individual and combined effects of intervention component(s) and thus also optimize the intervention for efficiency.

PA-monitors can facilitate intervention delivery and data collection. Numerous commercially available PA-monitors (e.g., Fitbit) are affordable, acceptable and useful to older adults,³⁶ and have the potential to facilitate PA.³⁷ Additionally, recent evidence suggests that PA-monitors, Fitbit OneTM in particular, provide accurate measurement of steps, PA duration and intensity.³⁸⁻⁴¹ There are no fall-reducing PA intervention studies that we are aware of, with the exception of our preliminary studies that describe integrating PA-monitors. Evidence about commercially available PA-monitors can be used to inform intervention design and measurement methods.

Community-based fall-reducing PA interventions have the potential to improve PA promotion efforts. Prior research suggests that community engaged research yields more meaningful collaborations; improved interventions that are more sustainable; and improved health outcomes on both individual and community levels.⁴² Fall-reducing PA interventions that are community-based provide a means for developing research-community partnerships, as well as interventions with potential to be more sustainable.

In sum, this proposal addresses two serious, common, and preventable public health problems: falls and low PA, by integrating strengths and limitations of prior research. The intervention combines an evidence-based fall-reducing PA protocol targeting leg strength and balance; plus key behavioral change strategies targeting motivational constructs. These key behavioral change strategies, which are empirically based and theoretically informed, are separated into two intervention components comprised of distinct sets of intervention strategies: interpersonal (e.g., fostering social support for PA; facilitating friendly social comparison) and intrapersonal (e.g., facilitating the development of goals and plans). The individual and combined effects of these components on long-term outcomes, and motivational constructs, will be tested using a factorial experiment. Commercially available PA-monitors will be integrated into the intervention and the accelerometers built in to the monitors will be used to objectively

measure PA. The successful implementation of this proposal relies on partnerships with community stakeholders, which our team has established over the last three years. This proposal's research will optimize a multicomponent intervention whose behavioral change strategies produce meaningfully sustained effects on increased PA, reduced falls, and improved QOL. This contribution will be significant because it is expected to foster the integration of biomechanically-oriented fall-reducing PA protocols with behavioral change strategies that impact health outcomes.

Innovation. The design of this proposal's study, and methods used to achieve its aims, are highly innovative. The design, driven by the inter-related problems of falls and low PA rates in older adults, engages the science of behavior change and gerontology to identify and test strategies that potentially motivate sustained PA, and in turn reduce falls and improve QOL. As illustrated in **Figure 2**, the conceptual model for this intervention includes critical elements that guide the serial assessment of mechanisms and outcomes, which will enable us to observe and describe intervention effects, as well as patterns of change over time. The design of this proposal is consistent with systematic approaches to optimizing behavioral change interventions that increase understanding of what works, when, and how; and that lead to effective, efficient, and translatable programs.^{43,44} Such approaches are a novel enhancement to existing fall-reducing PA protocols. Factorial experimental methods used within this proposal complement the design described here and allow us to directly test each aim's working hypotheses.³⁵

The proposed research is innovative, in our opinion, because it represents a substantive expansion of biomechanically-oriented fall-reducing PA protocols to a) examine which behavioral change strategies elicit sustained effects (e.g., 12 months) on increased PA, as well as on falls, and QOL; and b) explore underlying mechanisms of PA and falls.

Successful completion of this research is expected to strengthen PA promotion efforts in older adult populations by identifying strategies that support older adults to autonomously sustain increased PA, and by gaining an understanding of mechanisms that enable the application of our study results to other areas of health.⁴⁵

Figure 2. Intervention Conceptual Model

CHAPTER 3 - STUDY OUTCOMES

3.1 PRIMARY OUTCOME

The primary study endpoint, event, or outcome we will be evaluating or observing.

The **primary outcome** is the quantity of PA: the average minutes of total PA per week (light, moderate and vigorous intensities) measured objectively and via self-report.

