We believe participation in this research will yield benefits for participants. Mastery of physical activities within the Otago PA protocol will provide participants with skills and knowledge to practice these exercises safely at home or in other environments of their choice. The behavioral change strategies in the intervention have the potential to motivate participants continued engagement in PA. Participants will also receive a PA-monitor for self-tracking and support to use it as well as interpret its data.

CHAPTER 17 – DATA MANAGEMENT

17.1: DATA ANALYSIS PLAN

Statistical analysis. Descriptive statistics (means, standard deviations, ranges for continuous variables and counts/ percentages for categorical variables) will be used to summarize biologic, demographic, outcome, and exploratory measures by treatment arm, actual and projected accrual, attendance and retention rates, quality control data (e.g., missing data), and fidelity data. Tables, graphs and charts will be used to visualize data when appropriate. Enrollment summaries will be reviewed at weekly research staff meetings throughout enrollment phases and every month during non-enrollment phases. Differences by randomly assigned condition will be assessed with one-way ANOVA tests for continuous and Fisher's exact test or chi-square tests for categorical variables as appropriate. Any identified confounders will be adjusted for in subsequent analyses. All analyses will be pre-planned and conducted while masked to condition.

We will include all cases in analyses, regardless of intervention attendance rates or attrition. Missing data will be analyzed. We anticipate, based on preliminary research that the rate of missing data will be low and similar across conditions, but that it may be associated with severe illness that leads to dropout or inability to capture follow- up PA data. Thus, similar to preliminary analyses, we will conduct a sensitivity analysis of complete cases and imputing worst case carried forward.

Primary Aim: Intervention component effects on PA will be assessed using 2x2 full factorial ANCOVA models with duration of total PA as the outcome (average minutes per

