week). The factors, or independent variables, are interpersonal and intrapersonal components; each with two levels indicating exposure (No vs Yes). Different models will be developed for PA measured objectively. PA will also be measured via self-report. Each model will include baseline PA values as a covariate. Main and interaction effects of the components on the duration of PA will be tested immediately, 6 months, and 12 months post- intervention. Further, we will apply multilevel longitudinal data analyses to examine the variation of component effects across time-points (baseline; immediately post-intervention; 6 months' post-intervention; and 12 months' post- intervention), including interactions between components (e.g. interpersonal x intrapersonal x time), which will allow us to see when an older adult might benefit from additional support to maintain PA.

Secondary Aim: The secondary outcome of Falls will first be described using the number of falls, fallers, fall rate, and time to first fall post-intervention.⁷⁴ Given the expected distribution of falls, we will use negative binomial regression models to estimate the between-group difference in fall rates 12 months' post-intervention. Quality of Life data will be assessed using 2x2 full factorial ANCOVA and longitudinal analyses described for Aim 1 with total mean QOL as the outcome variable.

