Exploratory Aim: The exploratory aim of the study is to investigate the nature of relationships between receipt of one or more intervention component and outcome variables. We will assess if this study's intervention component(s) changed mediator variables, and in turn caused increased PA or reduced falls. In this study, the putative mediators of PA are Motivational Constructs: a) social support (support from family and friends for physical activity); b) readiness (Index of Readiness, Self-Efficacy for Exercise Scale); and c) self-regulation (index of self-regulation, goal attainment, Behavioral Regulations in Exercise Questionnaire-3). The putative mediators of falls are Physical Markers of Fall Risk: leg strength and balance (SPPB, Physical Function SF 6b). Using the general approach to mediation analysis described by MacKinnon,⁹⁶ we will assess the effects of intervention components on mediators, and the effects of mediators on outcomes, as well as the total direct and indirect effects of intervention components on PA and falls. Counterfactual approaches described by Vanderweele and colleagues⁹⁷ will be used if nonlinearities or interactions between exposure and mediator variables are observed.

Additional exploratory analyses: pain, medication, and sex as a biological variable:

Although this study is not designed to conduct confirmatory subgroup analyses of covid-19, pain, medication, or sex,^{98,99} we will conduct stratified, exploratory analyses to assess effect modification by these variables. We will report values for these variables as well as differences observed, which may be valuable for future research and meta-analyses

17.2: POWER ANALYSIS

Sample size and power. The primary aim of the proposed study is to detect clinically meaningful intervention effects on PA from baseline to 12 months' post-intervention. Meta- analyses in the field of PA and older adults describe standardized effect sizes that range from .18³¹ to .26⁹² which translate to 670 to 870 additional steps per day or 73 to 94 additional minutes of PA per week. Although these effects are small, they are considered to be clinically important in older populations whose overall activity levels are low; often sedentary.⁹³ Thus, we based our sample size estimates on a small

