standardized effect size of .20. We also anticipate 15% attrition at 12 months, based on our preliminary studies which showed 7% attrition at 6 months. Considering these assumptions, a sample size of 308 (77 per condition) will enable us to detect small but clinically meaningful main effects of the interpersonal or intrapersonal components as well as their interaction (effect sizes of .20), with 80% power, under a two-tailed hypothesis test at a significance level of .05.⁹⁴ This sample size will also enable us to detect medium to large effects on our secondary outcome of falls (fall rate ratios of .40 to .70), with 80% power, under a two-tailed hypothesis test, at a significance level of .05, which is consistent with prior research that shows Otago PA reduces falls (fall rate ratios 0.56 to 0.79).¹⁰

17.3: DATA INTEGRITY

Data Monitoring. Ongoing quality control procedures will be implemented for data collection, storage and processing. The data manager will conduct monthly monitoring of the study database and generate a report for the PI to review at team meetings. Standing agenda items for these meetings will include participant recruitment and retention, serious adverse events, unexpected adverse events, expected adverse events, protocol deviations, data integrity, and overall study conduct.

CHAPTER 18 – CONFIDENTIALITY

17.4: DATA SECURITY

Data Collection. All data from participants screened for the study will be entered and stored in an electronic study database. Designated research staff will collect and enter required data (written informed consent, responses to interview data) onto electronic study data forms. Screened participants who do not meet study eligibility will have specific screening data entered the study database as this data will be helpful in examining the patient population and feasibility of enrollment criteria and will include gender, age, race and reason for exclusion. All dates will be shifted and other Personal Health Information (PHI)--which in this study includes self-reported medical history, fall risk, and medication regimen--will be removed from the study database upon study completion. All data obtained from this study will be used for research purposes only and will not include data from electronic health records.

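### The primary outcome has two unranked measures, the three-time hypothesis has no matching power statement, and the Fitbit wear instructions contradict each other

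*Combined protocol and SAP*

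**What the plan says.** **Measures.** Section 3.1 gives one primary outcome, "the average minutes of total PA per week (light, moderate and vigorous intensities) measured objectively and via self-report". Section 17.1 says: "Different models will be developed for PA measured objectively. PA will also be measured via self-report". It adds "Each model will include baseline PA values as a covariate" and "All analyses will be pre-planned and conducted while masked to condition". Nothing ranks the two measures, requires both, or divides the .05 level in 17.2. The interview list in 5.2 includes the PASE, but nothing says which instrument yields self-reported minutes per week.

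**Times.** The primary hypothesis in 1.1 predicts "clinically meaningful increases in PA post- intervention (at all 3 time-points" for the interpersonal component. Section 17.1 says "Main and interaction effects of the components on the duration of PA will be tested immediately, 6 months, and 12 months" after the intervention. Section 17.2 states the aim as to "detect clinically meaningful intervention effects on PA from baseline to 12 months' post-intervention" and continues: "We also anticipate 15% attrition at 12 months, based on our preliminary studies which showed 7% attrition at 6 months". It then gives one figure: 308 participants, effect size .20, 80% power, two-sided .05.

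**Wear.** In 5.2, the baseline paragraph sets 10 hours a day as the least the monitor is to be worn. The later paragraph on objectively measured PA makes 10 hours the most. That later paragraph lists all four collection periods, baseline included. The process-evaluation text in 5.2 then carries the baseline procedures, apart from the practice week, forward to follow-up.

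**The concern.** A primary outcome with two measures needs a rule for when they disagree. Masked, pre-planned analysis does not supply one, because it does not say which measure decides. If the Fitbit and self-report results split, the trial has no agreed primary conclusion.

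The hypothesis speaks of three times, and the power statement gives one figure. If confirmation requires all three, the chance of achieving it is lower than that figure, and a failure could be misread as evidence of no effect.

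Recorded active minutes can rise with hours worn. A participant who follows a 10-hour ceiling has recorded minutes cut off, and one who follows a 10-hour floor does not. Mixed instructions would therefore make the primary measure less comparable between people and between visits.

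**Working it through.** **The plan's own figure.** There are 154 participants per factor level, or 131 after 15% loss (308 x .85 = 262). For a difference of d SDs, power = Phi(d x sqrt(131/2) - 1.96).

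- d = .20: Phi(1.62 - 1.96) = 37%.
- .20 read as Cohen's f (d = .40): Phi(3.24 - 1.96) = 90%.
- d = .20 with baseline adjustment: 80% is reached at a baseline correlation of about .82, which 17.2 does not state.

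So 80% depends on an unstated metric or correlation. That is a separate question; below, 80% is granted.

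**Two measures at one deciding time.** Let Z1 and Z2 be the two test statistics, with assumed correlation r.

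- Either may count: two-sided error = 1 - P(|Z1| < 1.96 and |Z2| < 1.96).
- Both must succeed: false increase = P(Z1 > 1.96 and Z2 > 1.96) under no effect.
- Power for both, if each alone has 80%: the same probability with each mean at 1.96 + .84 = 2.80.

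| r (assumed) | Either: two-sided error (nominal 5%) | Both: false increase (nominal 2.5%) | Both: power |
|---|---|---|---|
| .2 | 9.6% | .16% | 66% |
| .4 | 9.3% | .34% | 68% |
| .6 | 8.8% | .62% | 70% |

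As a check, independent tests under the either rule give 1 - .95² = 9.75%.

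**Three times, one measure.** Joint power = P(Z at all three times > 1.96), with an assumed common between-time correlation.

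- Equal loss: mean 2.80 at each time.
- Lower early loss: 7% at the immediate and 6-month visits (stated for 6 months in the preliminary studies; assumed for the immediate visit). Then n = 308 x .93 = 286, and the mean is 2.80 x sqrt(286/262) = 2.93, or 83% power at each early visit. The 12-month mean stays at 2.80.

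| Between-time correlation (assumed) | Equal loss | 7% early loss |
|---|---|---|
| .3 | 57% | 61% |
| .5 | 61% | 65% |
| .7 | 66% | 69% |
| .8 | 69% | 72% |

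As a check, independence with equal loss gives .8³ = 51%. Requiring all three times does not inflate error: under no effect, all three exceed 1.96 with probability at most .7% over this range.

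**Wear.** No arithmetic is needed. One paragraph of 5.2 sets a floor of 10 hours and another a ceiling of 10 hours. Both apply at baseline, so they cannot be instructions for different periods. Only exactly 10 hours satisfies both. The manual of operation cited in 14.1 cannot make both protocol statements true.

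**The case against.** **Fitbit already leads in substance.** Section 17.1 attaches its models to objective PA and says only that PA is also measured by self-report. Section 2.2 calls for effects on objectively measured PA and says the monitors' accelerometers will be used for that purpose. Section 17.2 gives the target effect in steps as well as minutes. This stands as evidence of intent, and a reader should not take 17.1 as plainly modelling both measures. But 3.1 still names both, and a hint does not set a hierarchy. The PASE is a plausible source for self-report, but no rule converts it to minutes per week.

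**Inflated error is not the plan's rule.** A reader might infer that the trial runs at nearly double its nominal error, or higher still if any measure at any time could count. The documents state no such rule. The word joining the measures in 3.1 is 'and', which fits requiring both at least as well. What stands is that the rule is missing.

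**The hypothesis is a prediction.** Section 1.1 predicts increases at three times; it does not state that significance is required at each. Section 17.1 tests each time and adds a longitudinal model. Because 17.2 uses the largest stated loss, its 80% could cover each earlier time singly if effects and variances are similar. This stands: the absence of joint power is a reporting gap.

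**Wear.** A reader might infer bias between conditions. Nothing shows wear differing by condition, and a shift common to all conditions cancels from the comparison.

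**Conclusion.** The point holds, as a change that should be made before unmasking. Three things follow from the text alone: the two measures in 3.1 are unranked, 17.2 does not describe the power to confirm increases at all three times, and 5.2 gives contradictory wear limits for the same periods.

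The sizes rest on assumptions. The 8.8-9.6% error applies only if either measure may count at one deciding time, with correlation .6 to .2. The alternative of requiring both costs power instead. The joint power of 57-69% (61-72% with lower early loss) applies only if all three times are required, 80% is granted at each time (at 12 months in the lower-loss case), and between-time correlation is .3-.8.

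A reader might also infer that the 80% is wrong. That is not concluded here, since it depends on the metric of the .20 and on a baseline correlation the plan leaves unstated. The wear conflict is the minor part: it affects the quality of the primary measure, and its size cannot be fixed from the documents.

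**What to change.** Before unmasking:

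1. **Measure.** In 3.1 and 17.1, name Fitbit total minutes per week as the sole primary measure. Make self-report supportive and name the instrument that gives its minutes. Cost: self-report can no longer carry the primary claim.
2. **Success rule.** State one rule for the interpersonal hypothesis and make 1.1, 17.1 and 17.2 agree. One option is all three times, each at .05 without adjustment, with joint power and its assumed correlations stated in 17.2. The other is 12 months as the primary time, which suits the power text, with the other two supportive. All three times stay reported either way, as the Primary Aim asks. Cost: the stated power may be less favourable, clearly so under the first option.
3. **Wear.** Reconcile the two paragraphs of 5.2 into one instruction, with 10 hours as a minimum for any remaining collection. Report inferred wear hours by condition and add one wear-adjusted sensitivity analysis. Fitabase holds minute-level data (section 17.4), but 5.2 lists intensity classes and steps, not wear, so worn hours can only be inferred. By March 2020 cohort 11 of 13 was already in week 6 of the intervention (section 4.1), so minutes lost to a 10-hour ceiling in data already collected cannot be recovered.

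All of this is wording plus modest programming and needs no new data.
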